2 STUDY OBJECTIVES

The primary and the secondary objectives of this clinical trial are defined as follows:

Primary objectives:

1. Biomarker discovery - define a set of differential epigenetic biomarkers that uniquely identify the following conditions: MM, pre-MM conditions [smoldering MM (SMM) and monoclonal gammopathy of undetermined significance (MGUS)], HL, aggressive NHL [diffuse large B cell lymphoma (DLBCL), FL, MZL, AML, MDS and control subjects with no malignant disease .
2. Validation – validating the discovery platform (HemaChip) as a diagnostic tool for various hematological malignancies.
3. Towards early detection - Patients, at risk of relapse tested periodically to evaluate early detection capability of the HemaChip.
4. Towards population screening - evaluate the sensitivity and specificity for screening in populations at risk for developing the investigated cancers: (i) elderly (>65 years old) at high risk to develop MM; (ii) first degree relatives of the conditions described above.

Secondary objectives:

1. Evaluate the correlation between epigenetic status and well-known prognostic markers, including known genetic markers.
2. Predict response to therapy.

Exploratory objectives:

1. Identify new therapeutic targets based on epigenetically modified genomic loci.
2. Provide prognostic information at pre-treatment and monitoring of MRD.

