4.3 Third stage

The last stage consists of screening of a larger group of subjects at risk to develop MM / lymphoproliferative disorder. This stage will include 400 elderly patients (>65 years old) and 500 first-degree relatives of patients (and in particular siblings). The screening, enrollment and sample collection can begin in the first stage of the trial, in order to meet the recruitment goals.

In all stages, the age and sex-matched subgroups will be considered and matched.

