4.4 Clinical follow-up

Subjects that serve as controls, subjects at risk (from the Third stage) and a subset of patients from the First and Second stage are expected to donate blood a single time. Following this donation, their participation will end.

For a subset of patients from the Second stage it is expected, after signing the informed consent forms, that serial samplings will be performed during the disease follow-up according to the standard clinical practice and/or recommended schedule and disease assessment plan (see Table 3).

All follow-up patients will be followed for a period of up to 36 months.

For this clinical trial, demographic and baseline parameters including sex, age, race, height and weight, medical history, smoking history and status, details of initial diagnosis and treatment history concomitant medications as well as adverse events (AEs) of special interest (see section 9.1), (serious) AEs related to study procedure, treatment for the disease, disease response and survival status will be collected (as applicable).

Subjects who complete the main study, may be followed up for their disease status, anti-cancer

treatments, concomitant medications, new primary malignancy and survival, following statistical review of the study results. Serial blood samplings will be performed during the long-term follow-up according to the standard clinical practice and/or recommended schedule and disease assessment plan (see Table 3).

A detailed plan for long-term follow-up beyond the main study will be provided as an amendment to this protocol.

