5 STUDY POPULATION

5.1 Number of subjects

First stage: at least 300 subjects.

Second stage: at least 1000 subjects.

Third stage: up to -900 subjects.

The sample size calculations and consideration are presented in section 10.4 below.

The number of participants in the study is described in Table 1 below.

Table 1. Number of participants

	1st Stage	2nd Stage*	3rd Stage*
	No. of Patients/Subjects (at least)	No. of Patients/Subjects (at least)	No. of Patients/Subjects (up to)
MM	30	250	-
MGUS	30	100	-
SMM	30	100	-
HL	30	100	-
DLBCL	30	250	-
FL	30		-
MZL	30		-
AML	30	100	-
MDS	30	100	-
Control (with no malignant disease)	30		
Subjects at risk	-	-	400 Elderly >65 500 First degree relatives

* The screening, enrollment and sample collection can begin in the first stage of the trial, in order to allow a maximum follow-up period for at-risk subjects as part of the study and to meet the recruitment goals.

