6.2 Schedule of events

The detailed summary of the evaluations and procedures planned in this study is presented in Tables 2 and 3.

Table 2. Schedule of events

Evaluation	Screening visit¹ (Day -28 to -1)	Baseline sample (Day 1 ± 28 days)	Follow-up visit² (sub-set of patients in Stage 2)
Signed consent form	X		
Assessment of eligibility criteria	X		
Assigning patient ID	X		
Assigning patient barcode	X		
Record medical history ³	X	X	
Record concomitant medications	X	X	X
Record demographics ⁴	X		
Record smoking history / status	X	X	X
Record prior anti-cancer treatments ⁵	X	X	
Record weight	X	X	X
Record heights	X		
Record baseline disease characteristics including prognostic profile ²	X		
MM lab profile for subjects at risk to develop the investigated hematological malignancies ⁶	X		
Blood sampling for central lab (JaxBio) ⁷		X ²	X ²
Disease response evaluation			X ²
Survival status			X
Record adverse events		X	X

¹ Screening visit can be performed at the same day as baseline sample.

² Refer to Table 3 for recommended schedule and disease assessment plan for follow-up patients in Stage 2.

³ Medical history will include details of initial diagnosis.

⁴ Demographics include sex, age and race.

⁵ Only for Secondary-AML, transformed FL and MZL conditions.

⁶ **In Stage 3.** MM lab profile will include SPEP and FLC, full chemistry and CBC.

⁷ Two (2) blood tubes for each sample will be collected and shipped. Refer to Study Manual.

HemaChip tests at the clinical sites ⁸		X ⁹	X ⁹
---	--	----------------	----------------

⁸ **In stages 2 and 3 of the clinical trial only.** The HemaChip and custom reagents will be distributed to partners' labs and all tests will be conducted at the clinical sites.

⁹ Two (2) blood tubes for each sample will be collected. One (1) for test at the clinical sites and the second as a backup for additional validation tests at JaxBio and TAU, as needed. Refer to Study Manual.

Table 3. Recommended schedule and disease assessment plan – Only for follow-up patients

Condition Visit	Baseline Characteristics and Assessments ¹	Follow-up for Disease Evaluation		Blood Sample for Central Lab/HemaChip at site ^{2,3}
		Disease Evaluation ¹	Recommended Schedule	

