the discovery array and this number of tests should suffice. Accumulation of additional data is expected in the next phases of the project in order to accurately tune the statistical analysis according to the data.

[figure not shown]

Figure 2. Required sample size for HemaChip, analyzed by Proportion sample size determination for binomial distribution (arcsine transformation, significance level = 0.05, test power = 0.8).

Stage 3: Screening at-risk cohorts

When calculating the sample size for the screening stage, the incidences of individual types of hematological malignancies were considered. The assumption is that the individual types will occur in the same proportion also in the risk cohorts of patients. We also consider the minimum number of samples with respect to the HemaChip and its expected sensitivity (as detailed in stage 2), and the known fact that the incidence of the hematological malignancies is about five percent in the risk cohort. Then, the sample population was determined to be approximately 7120. Such a screen is beyond the scope of this project but given that the tests performed side by side with standard diagnosis, the incidence rate is sufficient to derive initial performance metrics based on several hundred tests. Positive results will allow performing a large scale clinical study needed for screening purposes.

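### For the 500 first-degree relatives in Stage 3, screening sensitivity and specificity are sought for every listed condition, but only a myeloma blood panel at a single visit is scheduled as reference

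*Protocol*

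**What the plan says.** **Objective.** Protocol Section 2, primary objective 4, is to "evaluate the sensitivity and specificity for screening in populations at risk for developing the investigated cancers". It names two groups: elderly subjects at high risk of MM, and "first degree relatives of the conditions described above". The conditions listed there are MM, SMM, MGUS, HL, DLBCL, FL, MZL, AML and MDS. Section 3 makes sensitivity and specificity at each stage a primary endpoint.

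**Stage 3 population.** Section 4.3 describes "screening of a larger group of subjects at risk to develop MM / lymphoproliferative disorder", with 400 elderly subjects and 500 relatives.

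**Reference work-up.** Table 2, footnote 6 (Section 6.2), says of Stage 3: "MM lab profile will include SPEP and FLC, full chemistry and CBC". Section 7.1 repeats that the MM profile is done for at-risk subjects. Table 3, which holds the lymphoma and AML assessments, applies only to follow-up patients.

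**Comparator assumed in the sample size text.** Section 10.4 expects usable first performance figures "given that the tests performed side by side with standard diagnosis".

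**Follow-up.** Section 4.4 says of controls and Stage 3 at-risk subjects, after their single donation: "Following this donation, their participation will end". The synopsis (Duration of subject participation) and Section 6.1 agree. Yet the Table 1 footnote in Section 5.1 justifies early enrolment "in order to allow a maximum follow-up period for at-risk subjects as part of the study", and the Stage 3 paragraph of the synopsis (Methodology) gives the same reason.

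**The concern.** Sensitivity needs subjects known to have the disease, and specificity needs subjects known not to have it. A relative whose HemaChip result points to lymphoma has no scheduled test that could confirm or refute it, and a relative with a missed lymphoma has none that would reveal it. The sample size text leans on a standard diagnosis run alongside, but Table 2 and Section 7 schedule none for lymphoma, AML or MDS in Stage 3. Because participation stops at one draw, later diagnoses are not actively sought either.

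At stake is what Stage 3 can conclude on a primary objective. Section 1.2 says the results may be used for marketing approvals. A larger sample would not help, because the missing item is disease status and not precision.

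**Working it through.** **1. The plan's own figure.** Section 10.4 gives 356 subjects for 85% against a lower bound of 80% (significance level 0.05, power 0.8, arcsine). The text calls the 85% a specificity, but the surrounding argument concerns sensitivity. The one-sample, one-sided formula is

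n = [(z₀.₉₅ + z₀.₈₀) / (2·asin√0.85 − 2·asin√0.80)]² = 355.4, rounded up to 356.

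With 5% diseased in the risk cohort, 356 / 0.05 = 7120, the stated screening population. Both figures reproduce, so the arithmetic is not at issue.

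**2. Objective against scheduled reference, by arm.**

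| Arm | Conditions in objective 4 | Scheduled in Stage 3 | Protocol's own gold standard (Section 1) |
|---|---|---|---|
| 400 elderly | MM | SPEP, FLC, chemistry, CBC | Bone marrow biopsy |
| 500 relatives: MM, SMM, MGUS | yes | same panel | Bone marrow biopsy for MM |
| 500 relatives: HL, DLBCL, FL, MZL | yes | nothing specific | Lymph node biopsy |
| 500 relatives: AML, MDS | yes | CBC only; no smear or marrow | Marrow biopsy named for indicated conditions other than MM; AML and MDS not listed individually |

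Even for plasma-cell disease the panel does not separate MM, SMM and MGUS: Table 3, footnote 4, lists marrow plasma-cell percentage and FISH among the diagnostic items. What the panel can supply is one pooled category, a monoclonal protein or an abnormal FLC result.

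**3. Expected cases.** I treat the 5% in Section 10.4, which covers all haematological malignancies together, as the fraction diseased at the draw.

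- Relatives: 500 × 0.05 = 25 cases.
- Elderly: 400 × 0.05 = 20 cases.

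The documents do not give the share that is not plasma-cell disease. Assuming 25–75%, the unverified cases among relatives are 25 × 0.25 = 6.25 to 25 × 0.75 = 18.75, about 6 to 19.

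**4. What happens if unverified subjects are treated as disease-free.** The protocol states no such rule; this shows why one should be ruled out. Assume true sensitivity 85% and specificity 99% in the 500 relatives. There are 475 without disease, of whom 475 × 0.01 = 4.75 test positive. There are 25 × 0.85 = 21.25 true positives, so 26 positives in all. With u unverified cases:

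- apparent specificity = (475 × 0.99 + 0.15u) / (475 + u)
- apparent PPV = 0.85 × (25 − u) / 26

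| u | Apparent specificity | Apparent PPV |
|---|---|---|
| 0 | 99.0% | 82% |
| 6.25 | 471.19 / 481.25 = 97.9% | 15.94 / 26 = 61% |
| 12.5 | 472.13 / 487.5 = 96.8% | 10.63 / 26 = 41% |
| 18.75 | 473.06 / 493.75 = 95.8% | 5.31 / 26 = 20% |

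**5. Precision is a separate matter.** Even if all 25 cases were verified, 21 detected of 25 gives an exact 95% interval of 0.639 to 0.955. The protocol accepts limited precision. The missing reference is an additional problem.

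**The case against.** **The protocol claims little for this stage.** Section 10.4 says an adequate screen is out of scope and promises only initial metrics. That stands as an answer on precision. It does not supply a reference standard, and objective 4 remains primary.

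**The panel suits much of Stage 3.** This stands in part. For the elderly, objective 4 names only MM, and Section 4.3 mentions MM and lymphoproliferative disorder without AML or MDS. A reader might infer that the objective fails for all 900 subjects; the documents do not support that. Even on the narrower wording of Section 4.3, however, lymphoma in the relatives remains unverified.

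**Later diagnoses may still be captured.** Section 7 collects second primary malignancies until the trial completes, and Section 9.2 makes new malignancies events of special interest whenever they occur during the trial. Neither is limited by stage. But no contact with Stage 3 subjects is scheduled after the donation, so this is passive at best and sits badly with the end of participation. Follow-up after the main study is optional and deferred to a future amendment.

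**No rule says unverified subjects are disease-free.** Correct. A reader might infer that lymphoma calls would automatically become false positives and missed lymphomas true negatives. The protocol does not say so, and the SAP, which is not at hand, may say otherwise. The supportable statement is that status is unverified. An analysis plan cannot create disease status that was never collected.

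**The follow-up wording may refer to other patients.** In Section 4.2 the phrase about at-risk subjects can mean Stage 2 patients at risk of relapse, and Section 4.3 omits it. The conflict therefore rests on the Stage 3 paragraph of the synopsis and on the Table 1 footnote, which is attached to both the Stage 2 and Stage 3 columns.

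**Conclusion.** The point holds for the 500 relatives. Sensitivity and specificity for HL, DLBCL, FL and MZL cannot be estimated in Stage 3 as scheduled. For AML and MDS a CBC may raise suspicion but does not establish status. On the protocol's 5% and an assumed 25–75% share of non-plasma-cell disease, about 6–19 of 25 expected cases would be unverified. The CBC might flag some AML or MDS cases among them. For the 400 elderly the mismatch is smaller: the panel targets the named disease but is below the protocol's marrow-based standard, so it supports agreement with the panel and not diagnostic accuracy for MM.

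Separately, the statements on follow-up of at-risk subjects contradict each other and must be reconciled. The figures for apparent specificity and PPV rest on assumed test performance and on a scoring rule the protocol does not state; they illustrate a risk to exclude and do not predict the result.

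**What to change.** 1. **Narrow the claim in objective 4 and Section 10.4.** For Stage 3, state sensitivity and specificity only for plasma-cell disorder pooled, defined as a monoclonal protein or abnormal FLC on the panel. Describe this as agreement with the panel, and not as accuracy for MM, SMM and MGUS separately. For the other conditions report only the HemaChip-positive rate, and state that unverified subjects are not counted as disease-free. Cost: wording only.

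2. **Reconcile the follow-up text.** The Stage 3 paragraph of the synopsis and the Table 1 footnote must agree with the end of participation in the synopsis, Section 4.4 and Section 6.1, and with the collection of new malignancies until trial completion in Sections 7 and 9.2. Cost: wording, once the sponsor decides which is intended.

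3. **Optional supplement.** With amended consent, the sponsor could add one end-of-study record or registry check of haematological diagnoses. The other conditions would then be reported as diagnoses during follow-up, with follow-up time stated. Cost: a consent amendment and one data check per subject. Follow-up would be unequal by enrolment date, and undiagnosed disease would still be missed.

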6.2.1 Unscheduled visits

Unscheduled visits may be performed at any time during the study whenever necessary to assess for or to follow-up on AEs or as deemed necessary by the Investigator.

Evaluations and procedures to be performed at unscheduled visits, will be as clinically indicated at the Investigator's discretion, and may be based on those listed in Section 6.2, Schedule of events.

6.2.2 Response assessment

For MM patients, response assessments will be performed according to the International Myeloma Working Group (IMWG) Uniform Response Criteria for Multiple Myeloma²⁰ (See Appendix 2).

For HL and DLBCL patients, response assessments will be performed according to the 2014 Lugano criteria assessing FDG-PET/CT²¹ (See Appendix 4).

For AML patients, response assessments will be performed according to ELN guidelines 2022, NCCN guidelines 2021²² (See Appendix 5).

7 STUDY ASSESSMENTS

This section details the tests and the assessments that will be performed during the study (36 months).

AEs of special interest, (serious) AEs related to study procedures, concomitant medications, second primary malignancies and anti-cancer treatments will be collected from the time of signing of ICF until completion of the clinical trial.

7.1 Screening period

- Signed consent form
- Assessment of eligibility criteria
- Assigning patient ID
- Record medical history - Medical history will include details of initial diagnosis
- Record concomitant medications
- Record demographics - sex, age and race
- Record smoking history

- Record prior anti-cancer treatments only for Secondary AML, transformed FL and MZL conditions
- Record weight
- Record height
- Record baseline disease characteristics including prognostic profile - Refer to Table 3 for recommended schedule and disease assessment plan
- MM lab profile - will be performed for subjects at-risk in Stage 3.

7.2 Baseline sample

- Review medical history
- Review concomitant medications
- Review prior anti-cancer treatments
- Record weight
- Record smoking status
- Blood sampling for central lab (JaxBio). Two (2) blood tubes for each sample will be collected and shipped. Refer to study manual.
- Record AEs
- Hemachip tests at the clinical sites - **in stages 2 and 3 of the clinical trial only**. Two (2) blood samples will be collected. One (1) for testing at the clinical sites and the second as a backup for additional validation tests at JaxBio and TAU, as needed. Refer to Study Manual.

7.3 Clinical follow-up – sub-set of patients in Stage 2

- Review concomitant medications
- Record weight
- Record smoking status
- Blood sampling for central lab (JaxBio) - refer to Table 3 for recommended schedule and disease assessment plan. Refer to study manual.

- Record AEs
- Disease response evaluation (for follow-up patients in Stage 2) - refer to Table 3 for recommended schedule and disease assessment plan
- Survival status
- Hemachip tests at the clinical sites - **in stages 2 and 3 of the clinical trial only**. Two (2) blood samples will be collected. One (1) for testing at the clinical sites and the second as a backup for additional validation tests at JaxBio and TAU, as needed. Refer to Study Manual.

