MM	
 1. PCD diagnosis⁴ 2. Chemistry⁵ 3. Blood count⁶ 4. Virology⁷ 5. MM lab profile⁸ 6. Other baseline assessments⁹ 	
 1. Response will be evaluated according to IMWG criteria¹⁰ 2. MM lab profile⁸ 	MGUS: Once every 6 months SMM: Once every 3-6 months MM: Once every 2 months	X
HL, DLBCL, FL, MZL	
 1. Disease diagnosis¹¹ 2. Chemistry¹² 3. Blood count¹³ 4. Virology⁷ 5. Disease evaluation¹⁴ 6. Other baseline assessments¹⁵ 	
 1. Response will be evaluated according to Lugano 2014 criteria 2. Assessment of response^{14,16} 3. Assessment of B Symptoms 	
 1. First 2 Years: every 3 months 2. From the 3rd year: every 6 months 	X
AML	
 1. AML diagnosis¹⁷ 2. Chemistry¹⁸ 3. Blood count and smear¹⁹ 4. Coagulation tests²⁰ 5. Virology²¹ 6. Other baseline assessments²² 	
 1. Response will be evaluated according to ELN guidelines 2017/2022²³ 2. Molecular MRD when evaluable²³ 3. Blood count and chemistry 	
 1. Intensive chemotherapy 
 a. Day14 assessment²⁴ b. 3-5 weeks after induction therapy upon hematologic recovery c. Optional – upon hematologic recovery following each consolidation cycle d. If ASCT: 1 month after therapy 	X

¹ Will be performed locally at the clinical site.

² **In stage 1 of the clinical trial only**, Two (2) blood tubes for each sample will be collected in STRECK tube and sent to central lab (JaxBio). Refer to Study Manual. **In stages 2 and 3 of the clinical trial**, the HemaChip and custom reagents will be distributed to partners' labs and all tests will be conducted at the clinical sites. Two (2) blood tube for each sample will be collected, one (1) for test at the clinical sites and the second as a backup for additional validation tests at JaxBio and TAU, as needed.

³ Blood samples for Blood Sample for Central Lab/HemaChip at site – at diagnosis (baseline) and at all disease evaluation follow-up visits.

⁴ PCD diagnosis – date and age at diagnosis, type, ISS, R-ISS, BM Aspirate/Biopsy %PCs, FISH

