8 HEMACHIP

Operational requirements are divided to two periods:

Year 1: During the discovery phase, all tests will be conducted by JaxBio and TAU, which developed and optimized and routinely perform the procedure. At this stage, microarray measurements will be performed on a commercial platform that will be purchased from suppliers such as Agilent / Illumina. All reagents needed for the test will be either purchased or produced in-house.

Blood will be collected by all medical centers in cell-free DNA preservative tubes (STRECK) which stabilizes cell-free DNA for up to 14 days at room temperature. If needed, one ml of the blood will be immediately frozen for genomic DNA extraction. The required blood samples for the discovery phase will be shipped to JaxBio via FedEx. Cell-free tubes will be shipped at room temperature, while frozen blood will be shipped with ice packs to avoid thawing of the sample which may lead to DNA degradation. Import/export issues will be handled by JaxBio or TAU which holds a dedicated import department and has extensive expertise in all importing aspects. At JaxBio/TAU, plasma, serum and buffy coat will be separated, and cell-free DNA and genomic DNA will be extracted. Subsequently, methylation / hydroxymethylation labeling, microarray hybridization, detection and analysis will be performed.

Years 2-3: Throughout the second phase of the project, a custom targeted microarray, HemaChip will be developed and used for all tests. The HemaChip will be developed by Forschungszentrum für Medizintechnik und biotechnologie (FZMB) who specializes in microarray development, manufacturing and distribution. (FZMB) will be responsible for all aspects of distributing the

HemaChip to partners' labs including manufacturing, labeling, shipping etc. At this stage, all partners will purchase the reagents needed for performing the methylation labeling and HemaChip assays. Reagents that are produced at JaxBio/TAU will be validated in-house and shipped to partners' labs along with a validation kit to ensure performance. Quality control measures will be set up to ensure the same analytic condition for all laboratory partners. All tests will be conducted at the clinical sites. Additional validation tests will be conducted by JaxBio and TAU, as needed.

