10 STATISTICAL CONSIDERATIONS

10.1 Study design

Controlled study - This study aims to identify methylation patterns indicating the presence of cancer. Comparison to control participants with no malignant diseases is essential for identifying tumor-specific methylation patterns.

Open study - The current study is an open study where all participants are divided into known groups. For the first stage of the study, the group identification is essential for discovery of biomarkers for each disease type. Discovery stage will be based on empirical comparison between controls and patients diagnosed with various hematological cancers. Therefore, group identification is required for validation, comparison with state-of-the-art diagnosis and disease status.

The current study contains only one type of intervention and therefore randomized/crossover or parallel groups are inapplicable.

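### The protocol contradicts itself on when follow-up samples are run on the HemaChip, so response scoring and the relapse date are not secured against knowledge of the chip result

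*Protocol*

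**What the plan says.** **Testing after relapse.** Protocol section 4.2 and the synopsis (Methodology) state that follow-up blood and plasma stay in storage at the sites until a relapse has been diagnosed, and are then analysed on the HemaChip in retrospect. Section 4 likewise describes relapse patients as having their earlier samples analysed retrospectively.

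**Testing at the visit.** Table 2 marks the site HemaChip test at both the baseline and the follow-up visit for Stages 2 and 3. Section 7.3 lists "Hemachip tests at the clinical sites" for the follow-up visit and splits the tubes: "One (1) for testing at the clinical sites and the second as a backup for additional validation tests at JaxBio and TAU, as needed". Table 3, footnotes 2 and 3, repeats the site testing and ties blood sampling to every disease evaluation visit. Section 8 adds for this period: "All tests will be conducted at the clinical sites". None of these places mentions storage until relapse.

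**The reference at the same visit.** Section 7.3 also lists "Disease response evaluation (for follow-up patients in Stage 2"), and Table 3, footnote 1, says of the baseline and disease assessments: "Will be performed locally at the clinical site". Under section 6.2.1, unscheduled visits may take place for adverse events or "as deemed necessary by the Investigator".

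**Openness and Stage 3.** Section 10.1 says: "The current study is an open study where all participants are divided into known groups". For Stage 3, section 10.4 rests its initial performance metrics on several hundred tests, "given that the tests performed side by side with standard diagnosis".

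**The concern.** Accuracy and lead time mean what they claim only if the reference (relapse, response or diagnosis) is set without knowledge of the index test. If site staff have the chip result while scoring response, a chip-positive patient may be examined sooner or more thoroughly than a chip-negative one. Two effects follow:

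- Disease found because the chip was positive counts as a true positive, while disease missed in chip-negative patients stays unseen. Observed sensitivity rises.
- Work-up prompted by the chip brings the relapse date forward. Lead time is the interval from the first positive sample to that date, so it would then depend partly on the test.

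The exposed results are early relapse detection (primary objective 3), the response-to-therapy endpoint (secondary) and, to a smaller degree, screening sensitivity and specificity (primary objective 4).

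**Working it through.** **Step 1. Can the chip result exist before the reference is set?**

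- *Stage 2 baseline diagnosis:* no. Section 5.2.1 enrols patients who already have the diagnosis.
- *Stage 2 follow-up under section 4.2:* no. Relapse is diagnosed first and the chip is run afterwards.
- *Stage 2 follow-up under Table 2 and section 7.3:* yes. The site chip test and the response evaluation belong to the same visit.
- *Stage 3:* possible but limited. The stated reference is a laboratory panel (SPEP, FLC, chemistry, CBC) at screening, which may fall on the sampling day. Participation ends after one donation. The step from an abnormal panel to a diagnosis is not described.

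The answer for follow-up therefore depends on which section a site follows.

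**Step 2. The protocol's own sample size figure.** The nearest stated figure is 356 subjects for the validation stage (section 10.4: 85% against 80%, arcsine, alpha 0.05, power 0.8). With n = ((z_alpha + z_power) / (2·asin√0.85 − 2·asin√0.80))², one-sided alpha gives 355.4, so 356; two-sided alpha gives 451.2. The figure reproduces one-sided and is not in dispute here.

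**Step 3. Illustrative size where the reference can depend on a known chip result.** Let s be true sensitivity, d the probability that the reference finds disease in chip-positive cases, and r the same in chip-negative cases.

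Observed sensitivity = s·d / (s·d + (1 − s)·r)

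The rates r and d are assumptions; the protocol gives none.

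| s | r = 0.60, d = 0.75 | r = 0.60, d = 0.90 | r = 0.90, d = 0.95 |
|---|---|---|---|
| 0.70 | 0.525/0.705 = 0.745 | 0.630/0.810 = 0.778 | 0.665/0.935 = 0.711 |
| 0.80 | 0.600/0.720 = 0.833 | 0.720/0.840 = 0.857 | 0.760/0.940 = 0.809 |
| 0.85 | 0.6375/0.7275 = 0.876 | 0.765/0.855 = 0.895 | 0.8075/0.9425 = 0.857 |

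In whole percentages, a true 70% is observed as 74–78%, 80% as 83–86% and 85% as 88–89%. In the milder scenario the gain is about 1 point. If d = r, the formula returns s and there is no bias.

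**Step 4. Stage 3 by a second route.** Section 5.1 gives up to 900 subjects and section 10.4 about 5% incidence, so 900 × 0.05 = 45 cases. Assume sensitivity 0.80, specificity 0.95 to 0.99, and a share f of discordant reference results resolved toward the chip. At specificity 0.95 and f = 20%:

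- False positives: 855 × 0.05 = 42.75. Apparent true positives: 36 + 0.2 × 42.75 = 44.55.
- False negatives left: 9 × 0.8 = 7.2.
- Apparent sensitivity: 44.55/51.75 = 0.861. At specificity 0.99 it is 37.71/44.91 = 0.840.

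At f = 5% the range is 0.810–0.817, and at f = 10% it is 0.820–0.833. Apparent specificity rises by at most 0.01.

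**The case against.** The best answer is section 4.2 itself. If follow-up samples are tested only after relapse is diagnosed, no chip result can move the relapse date, and the list in 7.3 may simply show what belongs to a visit without fixing when the chip is read. That reading is possible, and under it the follow-up problem disappears. But Table 2 and 7.3 place the test itself, not just the blood draw, at the visit and give one tube to it, so the protection is not secured.

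Three stronger readings are tempting and are not supported:

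- *That the chip can influence the reference diagnosis throughout.* Stage 2 diagnoses precede enrolment. In Stage 3 the stated reference is mainly a laboratory panel at screening, no chip-triggered work-up is described, and participation ends after one donation.
- *That the open design means results go to clinicians.* Section 10.1 uses the term for known group membership. No section says that results are returned to treating staff; some tests may run in partners' laboratories, and section 10.2.1 says samples are anonymised. The Study Manual, which is not available, may regulate release. What stands is that the protocol itself does not withhold results.
- *That the bias could use up the 5-point margin (85% against 80%).* That margin sizes the validation stage, which tests patients already diagnosed, where this bias is zero.

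The discretion in section 6.2.1 does not mention chip results. It shows only that the timing of assessments is not rigid.

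**Conclusion.** The point holds in limited form. The protocol is inconsistent on when follow-up samples are tested, and nothing in it keeps chip results from those who score response or declare relapse. If section 7.3 is followed, the relapse date, the lead time and the response endpoint would not be independent of the test. If section 4.2 is followed, relapse and lead time are protected. Stage 3 carries a smaller risk of the same kind, and the Stage 2 baseline diagnosis carries none.

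The size is illustrative only and rests on assumed detection rates: between about 1 and 8 points of sensitivity in the scenarios of Step 3, and zero wherever the reference is fixed before the chip is run. The contradiction itself needs no assumption.

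**What to change.** 1. Reconcile section 4.2 and the synopsis with Table 2, Table 3 (footnotes 2 and 3) and section 7.3, so that one statement says when follow-up samples are run on the chip.
2. State in sections 7.2, 7.3 and 10.1 that the laboratory holds HemaChip results and does not release them to staff who score response, declare relapse or make the Stage 3 reference assessment until that assessment is locked in the eCRF.
3. Log any earlier release, and repeat the accuracy and lead-time analyses without those subjects as a sensitivity analysis.

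The cost is a short protocol amendment and a release rule for the laboratory and eCRF; no extra visits or samples are needed. The drawback is that sites do not see chip results in real time.
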